Sample Size: Sample size calculation was based on the hypotheses associated with the Effectiveness component of RE-AIM and our prior research.^{8,10,12,22,23,29,77} With regard to facility level outcomes, our prior work resulted in effect sizes of 0.9 for environmental and policy changes.^{22,76,120} With the proposed sample size of 50 facilities, the statistical power for these two measures will be adequate (>.90 for both outcomes based on our analysis plan). For resident level outcomes, person-centered approaches resulted in a small intervention effect (Cohen's $d=0.19$) to maintain or improve BPSD, function, wellbeing or experiencing adverse events.^{8,10,12,22,23,29,77} Given a two-tailed alpha of 0.05, an estimated intra-class correlation coefficient (ICC) between clusters (facilities) of 0.02, a correlation coefficient between repeated measures (baseline, 4 and 12 months) of 0.6, and assuming even dispersion of means, a total sample of 500 residents will provide sufficient power ($\geq .80$) to detect the small effect size for group differences.¹²¹ Our prior research showed a 20% rate of attrition over 12 months.^{8,77} Therefore, we anticipate that a total of 625 residents from 50 nursing homes will be sufficient to demonstrate outcomes. To achieve this sample we will recruit 12-13 residents in each facility.

Setting: Nursing homes will be invited and eligible to participate if they: (a) agree to actively partner with the research team to change practice; (b) have at least 100 beds; (c) identify a RN, LPN or CNA to be the Champion; and (d) are able to access email and websites via a phone, tablet or computer. Recruitment of facilities will be done by mailing invitations to eligible facilities within the two states followed by telephone calls. We will also post invitations on relevant websites (see letters of support). This approach has been used successfully in our prior work.²² Fifty percent of the facilities we invited participated.²² Currently there are 152 nursing homes of appropriate size in Maryland and 439 in Pennsylvania. Given the regulatory climate with respect to dementia care in nursing homes, we are confident we will be able to engage 25 facilities per state.

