Behavioral Symptoms (Effectiveness): Depressive symptoms will be measured using the *Cornell Scale for Depression in Dementia (CSDD)*^{139,140}. CSDD is a 19 item survey that assesses depressive symptoms in individuals with dementia. There is evidence of reliability and validity of the CSDD.¹³⁹⁻¹⁴¹ Aggressive and/or resistive behaviors during care activities will be measured using the *Resistiveness to Care Scale*,¹⁴² a reliable and valid 13 item Likert scale that assesses residents' behaviors during activities of daily living. Agitated

behaviors will be measured using the *Cohen-Mansfield Agitation Inventory (CMAI)*,^{143,144} a survey of disturbing behaviors commonly found in residents with dementia. The 14 item version CMAI uses a 5-point Likert scale to rate the frequency of behavioral symptoms.^{144,145} Prior use supported evidence of reliability and validity.^{144,145}

Function (Effectiveness): *The Barthel Index (BI)*¹⁴⁶ is a 10 item measure of performance of activities of daily living with evidence of internal consistency, inter-rater reliability and validity.^{146 147} Items are weighted to account for the amount of assistance required. A total score of 100 indicates complete independence.

Quality of Life: will be measured using the *Quality of Life-AD (QoL-AD)*¹⁴⁸ scale. The QoL-AD is a 13 item reliable and valid instrument designed to rate the resident's quality of life from the staff perspective. Examples of items include physical condition, mood, relationships and participation in meaningful activities. Ratings are obtained on a 4 point scale (1= poor to 4=excellent) and total scores range from 13-52.¹⁴⁸

Adverse Events (Effectiveness): will be based on data obtained from medical records and designated individuals within the facilities (e.g., quality assurance nurse). Adverse events will include falls and transfers to hospitals or emergency rooms and physical restraint use. Baseline will include the four months prior to treatment implementation; 4 month will include those between baseline and 4 months; and 12 month those that occur between 4 months and 12 months post implementation of the intervention. Restraint use will be based on the reliable Minimum Data Base 3.0 definition of assessment for use of restraints.¹⁴⁹⁻¹⁵¹

Data Analysis:

Aim 1: To implement and test the implementation of EIT-4-BPSD.

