Descriptive statistics including measures of central tendency, dispersion and appropriate visualization approaches (e.g., box plots and spaghetti plots) will be performed on each outcome variable for residents and facilities. This will be done to ascertain distributional characteristics and ensure that the assumptions (e.g., normality) associated with the planned statistical procedures are met. When necessary, transformations will be performed. All analyses will be done using an intent-to-treat philosophy. Baseline characteristics (both resident level and facility level) will be compared between intervention and control groups and the relevant variables (e.g., age) that differ by group will be included as covariates in hypotheses testing. In particular we will utilize constructs known to correlate with BPSD including gender, pain, health status and cognitive and functional impairment. Linear mixed models (LMMs)¹⁵³ for longitudinal data (baseline, 4 and 12 months) will be used to assess the intervention effect on continuous outcomes (i.e., function, behavioral symptoms, and quality of life) accounting for clustering of residents that may occur within the same facility and correlations between repeated measurements of each resident. Mixed-effect Poisson regression [i.e., Generalized Linear Mixed Model

(GLMM)] will be conducted to assess the effect of the intervention on count outcomes (i.e., number of adverse events including number of falls, hospitalizations and emergency room visits, restraint use). The fixed effects included in the models will be treatment group (EIT-4-BPSD versus EO), time (baseline, 4 and 12 months), group-by-time interaction term and the aforementioned relevant covariates (e.g., age). Random effects will include facilities and residents.

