The hypothesis will be tested by evaluating the interaction term for each outcome variable. Similar LMMs will be used to compare changes in facility level measures (i.e., environments, policies) from baseline to 12 months with only facility included as random effects. For each hypothesis, exploratory analyses will be performed to assess model assumptions. Post-analysis diagnostic measures (e.g., residuals) will be explored to assess model fit. All tests will use a 5% significance level. The use of LMM will provide flexibility with regard to assumptions related to the covariance structure of the residuals and the presence of missing data for the repeated measures.¹⁵⁴ Missing data. In prior research we had 20% rate of attrition at the resident level and 10% of facilities.^{22,23} If there is significant dropout, we will identify baseline characteristics that differ between persons or facilities that drop out. Maximum likelihood methods will be used for primary analyses, which address non-informative dropout (missing at random [MAR]). If "informative" dropout appears possible, we will consider sensitivity analyses that involve adding these relevant baseline covariates to make the MAR assumption more plausible.¹⁵⁵ Qualitative data will be collected to inform effectiveness outcomes.

Adoption: Staff Adoption: Descriptive statistics will be done to evaluate the number of Internal Champions and Stakeholder team members participating in initial face-to-face training and monthly meetings among the 25 facilities randomized to EIT-4-BPSD. We will also consider improvement in scores on the Use of Behavioral Interventions for BPSD measure at each testing time point as evidence of adoption among staff. Facility Adoption: Facility adoption will be based on changes in environments, policies, and care plans of residents at 4 and 12 months post implementation of EIT-4-BPSD such that there is at least 1 item changed in each assessment area. Further we will describe differences among EIT-4-BPSD facilities that demonstrate adoption (based on changes in environments, policies and care plans) early (the first 4 months) versus late adopters (between 5-12 months) versus those that are non-adopters (no change by 12 months). Predictors such as facility characteristics will be compared across the three potential times of adoption (early, late, nonadopters).

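### Restraint use is a state but is assigned a Poisson count model, and linked falls, ER visits and admissions have no counting rule, so the H1 adverse-event tests may not run at 5%

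*Combined protocol and SAP*

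**What the plan says.** Under Resident RE-AIM Measures, the Adverse Events entry is labelled an Effectiveness measure and reads "Adverse events will include falls and transfers to hospitals or emergency rooms and physical restraint use". Hospital and ER transfers form one category there. The same entry adds: "Restraint use will be based on the reliable Minimum Data Base 3.0 definition of assessment for use of restraints". Counting windows are the four months before implementation, baseline to month 4, and month 4 to month 12.

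Under Data Analysis, Aim 1, Effectiveness, a mixed-effects Poisson regression is planned for count outcomes, given as the "number of adverse events including number of falls, hospitalizations and emergency room visits, restraint use". Facility and resident are random effects. The group-by-time interaction is tested outcome by outcome, and "All tests will use a 5% significance level". Residual diagnostics are planned, but no alternative to the Poisson model is named. For resident outcomes only linear and Poisson mixed models appear, so there is no model for a yes/no outcome. H1 includes the claim of fewer adverse events.

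The supplied text does not say whether the components are added together, how a fall that leads to an ER visit and an admission is counted, or in what unit restraint use is recorded.

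**The concern.** A Poisson model needs something that is counted. Restraint use measured by an assessment is present or absent, and it tends to persist in the same resident. Its variability is then much smaller than Poisson, standard errors are too large, and a real reduction would be hard to detect.

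The other count outcomes can fail in the opposite direction. If one incident produces several counted events in the same window, the count varies more than Poisson. A resident or facility intercept describes a tendency that is constant over time, so it does not absorb bundles that occur within a window. Standard errors are then too small and the test rejects too often. A total would also weight a fall by whether staff sent the resident out, so a change in transfer practice would look like a change in harm.

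**Working it through.** **1. The plan's own figures.** The Sample Size section states that "a total sample of 500 residents will provide sufficient power". Inflating for 20% attrition gives 500/(1 − 0.20) = 625, or 625/50 = 12.5 per facility, as planned. One analysis that reaches the stated power is the baseline-adjusted mean of the two follow-ups:
- design effect: 1 + (10 − 1) × 0.02 = 1.18
- variance factor at correlation 0.6: (1 + 0.6)/2 − 0.6² = 0.44
- standard error: √(4 × 0.44 × 1.18/500) = 0.0644
- power for d = 0.19: Φ(0.19/0.0644 − 1.96) ≈ 0.84

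This rests on a standardized difference and contains no event rate, so the present point does not change it. The only stated figure for the count outcomes is the 5% level.

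**2. The two sections side by side.**

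| Component | Measures section | Data Analysis |
|---|---|---|
| Falls | named | counted |
| Transfers | one category, hospital or ER | hospitalizations and ER visits both named |
| Restraint | assessment of use | listed under the Poisson model |

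**3. Restraint as yes/no under Poisson.** Let p be prevalence and s the chance that a restrained resident is still restrained in the next window (both assumed). The correlation one window apart is r = s − p(1 − s)/(1 − p), and two windows apart it is r². For a change between windows, Poisson given the resident assumes variance 2p. The true variance is 2p(1 − p)(1 − correlation). The ratio is (1 − p)(1 − correlation), and the true level is 2(1 − Φ(1.96/√ratio)).
- p = 0.05, s = 0.8: correlations 0.789 and 0.623. Month 4 against baseline: ratio 0.200, level below 0.0001. Month 12 against baseline: ratio 0.358, level 0.001.
- p = 0.05, s = 0.5: correlations 0.474 and 0.224. Ratios 0.500 and 0.737, levels 0.006 and 0.022.

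In simulation the joint two-degree-of-freedom interaction test had a true level of about 0–1.2% over p = 2–10% and s = 50–80%. As the last figure shows, the single month-12 contrast can reach about 2% at the lowest persistence.

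**4. Linked events, closed form.** Let K be the number of counted events per incident and φ = E[K²]/E[K]. The true level is 2(1 − Φ(1.96/√φ)) on 1 df and 0.05^(1/φ) on 2 df. Let e be the share of falls leading to an ER visit and h the share of ER visits leading to admission (both assumed).
- *Total, one transfer category:* φ = (1 + 3e)/(1 + e). For e = 0.05, φ = 1.095 and the level is 6.1% (1 df) or 6.5% (2 df). For e = 0.30, φ = 1.462, giving 10.5% or 12.9%.
- *Total, ER visit and admission counted separately:* φ = (1 + 3e + 5eh)/(1 + e + eh). For e = 0.05, h = 0.3, φ = 1.150, giving 6.8% or 7.4%. For e = 0.30, h = 0.5, φ = 1.828, giving 14.7% or 19.4%.
- *Transfers alone, ER visit and admission counted separately:* φ = (1 + 3h)/(1 + h). For h = 0.3, φ = 1.462, giving 10.5% or 12.9%. For h = 0.7, φ = 1.824, giving 14.7% or 19.3%.

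These are not bounds: e = 0.30 with every ER visit admitted gives φ = 2.125 and 17.9% or 24.4%.

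**5. Simulation with no treatment effect.** Assumptions: 500 residents in 50 facilities, resident and facility random intercepts, windows of 4, 4 and 8 months, 0.15 falls and 0.04 other transfers per resident-month, h = 0.4, e from 5% to 30%. The interaction was tested by Poisson conditional on the resident.

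| Outcome | 2 df | 1 df |
|---|---|---|
| Falls alone | 4.7% | 4.8% |
| Total, one transfer category | 6.6–11.6% | 6.5–10.2% |
| Total, ER and admission separate | 9.4–18.2% | 8.2–14.9% |

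The simulation differs from step 4 because it also includes transfers not caused by falls. Adding yes/no restraint to the last total at e = 10% gave 9.7–10.7% (2 df), against 11.9% without it. Yes/no restraint therefore adds no inflation.

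**The case against.** The strongest reply is that the plan never says it adds anything. It speaks of count outcomes in the plural and tests the interaction outcome by outcome. Adverse events may simply be a heading, as behavioral symptoms is a heading for three separate scales. The list can also be read as three slots that match the measures section: falls, hospital and ER use together, and restraint. On that reading falls keep their 5% level and no fall is counted twice across types. The planned distributional and residual checks might reveal overdispersion. The measurement level of each measure is said to be in Appendices E and F, which are not in the text available to me and may settle the restraint unit.

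Most of this stands, and it rules out several stronger conclusions that a reader might draw:
- That the plan sums the components is one reading of the sentence, not a statement in it.
- That a fall counts three times needs both summing and separate ER and admission counts. With the single transfer category the maximum is two.
- That restraint is tallied by day is nowhere stated, and an assessment definition points away from it.
- That the Poisson model for restraint inflates false positives is not so for a yes/no record, where the test is conservative.
- That a safety comparison is at risk misplaces the outcome, which belongs to effectiveness hypothesis H1.

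Two things survive the reply. Restraint use is listed under a Poisson model even if every outcome is analysed separately. And a separate transfers model still over-rejects if an ER visit and its admission count as two, which the visible text does not exclude. Diagnostics with no named remedy do not settle either.

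**Conclusion.** The point holds as a mismatch between model and measure for restraint use, and as a missing counting rule for linked events. It does not show that the adverse-event comparison is wrong as planned. If restraint is yes/no per window, the nominal 5% joint interaction test has a true level of about 0–1%, given assumed prevalence of 2–10% and persistence of 50–80%. If a total is tested, or an ER visit and its admission are counted separately, the nominal 5% test runs at roughly 7–19%, given 5–30% of falls leading to an ER visit and about 30–70% of ER visits leading to admission. The documents give no event rates, so these sizes are conditional; the direction of each error follows from the structure of the counts. Falls alone keep 5%. The sample size of 500 evaluable and 625 enrolled residents is unaffected.

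**What to change.** Make the Adverse Events entry and the Data Analysis paragraph agree:
- Test falls and transfer episodes as two separate Poisson count outcomes.
- Count an ER visit that leads to admission as one transfer episode.
- State that no summed adverse-event total is tested.
- Take restraint use out of the Poisson list. Analyse any use at each assessment (yes/no) with a mixed-effects logistic model with the same fixed and random effects, or report it descriptively if it is rare.

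It would be sensible in the same edit to name what follows if the residual checks show overdispersion in falls or transfers, for example a negative binomial mixed model.

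The cost is a wording change and one linking field on the abstraction form (whether an ER visit ended in admission). Each outcome will have fewer events than a total would, and the restraint model may prove estimable only descriptively.

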Real World Experience and Pilot Testing EIT-4-BPSD: Our team has expertise with regard to clinical work ([name], [name], [name]), administration ([name]) and regulations ([name]), and implementation of relevant innovative approaches to care (all investigators) in nursing homes. In addition, we have expertise in the education of minorities and nursing assistants([name], [name], [name], [name], [name]) and using qualitative methods ([name], [name], [name]) (see biosketches). We have pilot tested the EIT-4-BPSD in two facilities (one in Maryland and one in Pennsylvania) for feasibility and demonstrated that sites are willing to identify a Champion and Stakeholder team, engage in monthly face-to-face meetings (100% participation of stakeholders) and weekly email interactions (100% participation). We implemented all components of the intervention, recruited residents (recruitment rate of 50%) and completed measures without being burdensome to residents or staff. Building on our extensive preliminary work we will test EIT-4-BPSD in 50 nursing homes in Maryland and Pennsylvania.

Methods

Design: To achieve our Aims we will use a Hybrid III pragmatic cluster randomized clinical trial³² for two reasons: (a) implementation of EIT-4-BPSD requires a facility-wide approach; and (b) we need to prevent treatment contamination that might occur if we randomized within sites. Fifty nursing homes will be randomized to treatment (EIT-4-BPSD) or Education-Only Control (EO) using permuted-block randomization. Assignment will be concealed until after the facility consents to participate. Outcomes at the resident and facility level will be evaluated. Resident outcomes will be obtained at baseline, 4 and 12 months post implementation of the intervention. Facility outcomes will be obtained at baseline and 12 months post initial implementation. We will also examine Maintenance in EIT-4-BPSD facilities at 24 months post implementation.

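### As listed, the facility random effect drops out of the group-by-time test for continuous resident outcomes, so any change shared within a facility is left out of the error term

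*Combined protocol and SAP*

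**What the plan says.** Under Methods, Design, facilities are the unit of randomisation, 50 in all. The Adoption paragraph gives 25 to EIT-4-BPSD, which leaves 25 for Education-Only.

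Under Data Analysis, Effectiveness, function, behavioural symptoms and quality of life are analysed by linear mixed models at baseline, 4 and 12 months. Fixed effects are group, time, their interaction and covariates. On the random part the plan says "Random effects will include facilities and residents", and it describes the models as "accounting for clustering of residents that may occur within the same facility". On the test: "The hypothesis will be tested by evaluating the interaction term for each outcome variable", at 5%.

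Three further statements bear on the point. The plan credits mixed models with "flexibility with regard to assumptions related to the covariance structure of the residuals". It adds "Post-analysis diagnostic measures (e.g., residuals) will be explored to assess model fit". On estimation, "Maximum likelihood methods will be used for primary analyses". It names no facility-by-time effect, facility slope, cluster-robust variance or facility-based degrees of freedom.

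**The concern.** The interaction compares the arms on change. A facility intercept is the same at every visit, so it subtracts out of change, as does a resident intercept. What remains as error is the visit-to-visit residual of individual residents, treated as independent between residents of the same home. The adjustment therefore works for outcome levels but not for the quantity tested.

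If residents of a home tend to move together, 10 residents carry less information on change than the model assumes. The test is then anti-conservative and 95% intervals under-cover. The plan gives some reason to expect shared movement:

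- **Both arms:** assessments draw on the staff on duty (Procedure for Assessing Outcomes), QoL-AD is rated from the staff viewpoint (Resident RE-AIM Measures), and staff turnover is anticipated (Strengths and Limitations).
- **Intervention arm only:** implementation is tailored to each facility (Significance).

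**Working it through.** **Inputs from Sample Size.** Intraclass correlation 0.02; correlation between repeated measures 0.6; two-sided alpha 0.05; 500 residents in 50 facilities, so 500/50 = 10 per facility. The enrolment figure reproduces: 500/(1 − 0.20) = 625. Total variance is set to 1.

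**Assumption.** Let s be the share of the 0.02 facility variance that is stable over time. The documents do not give it, so a range is shown.

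**Step 1: the intercepts cancel.** With no drift the residual variance is 1 − 0.6 = 0.40. The variance of the 12-month contrast is (2/25)(2 × 0.40/10) = 0.0064, a standard error (SE) of 0.080. Raising the facility correlation from 0.02 to 0.10 or 0.30, with the 0.6 held fixed, leaves it at 0.0800. With 12 residents per facility and 20% dropout it is 0.0797 at 0.02 and 0.0793 at 0.30. With no drift the planned 5% level is reproduced.

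**Step 2: add shared change.** The facility-by-time variance is b = 0.02(1 − s) and the residual variance is e = 0.38 + 0.02s.

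- True variance of the contrast: (2/25)(2b + 2e/10).
- Residual variance that the intercept-only model estimates: [96(e + 10b) + 900e]/996. Here 96 = 48 × 2 degrees of freedom lie between facilities within arms, and 900 = 450 × 2 between residents within facilities.
- With V the ratio of true to model variance, the size of the single-contrast test is 2[1 − Φ(1.96/√V)], and that of the 2-df interaction test is 0.05^(1/V).

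Example, s = 50%: b = 0.01 and e = 0.39. True variance is 0.08 × (0.02 + 0.078) = 0.00784. The model residual is (96 × 0.49 + 900 × 0.39)/996 = 0.3996, so the model variance is 0.08 × 0.2 × 0.3996 = 0.00639. V = 1.226 and √V = 1.11, giving sizes of 7.7% and 8.7%.

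| Stable share | True SD / model SE | Both arms drift: 12-month / 2-df | One arm drifts: 12-month / 2-df |
|---|---|---|---|
| 100% | 1.00 | 5.0% / 5.0% | 5.0% / 5.0% |
| 90% | 1.02 | 5.5% / 5.7% | 5.3% / 5.3% |
| 80% | 1.04 | 6.0% / 6.4% | 5.5% / 5.7% |
| 50% | 1.11 | 7.7% / 8.7% | 6.3% / 6.8% |
| 0% | 1.20 | 10.4% / 12.7% | 7.7% / 8.7% |

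The SD/SE column is for drift in both arms.

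**Step 3: dropout and estimated variances.** Simulating the planned maximum likelihood fit (625 residents, 10% lost by 4 months and 20% by 12, 10,000 datasets per setting, drift in both arms) gave 12-month sizes of 5.2%, 5.7%, 6.5%, 8.0% and 10.4%. Loss of whole facilities was not modelled.

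**Step 4: the simplest repair is not enough.** A single-variance facility-by-time effect assumes drift that is independent and equally variable at each visit. Suppose drift is linear instead, with facility variance D in 12-month change. The visits 0, 4 and 12 have a sum of squares of 74.67 about their mean, so the single term estimates (74.67/2)/144 × D = 0.259D, where the contrast needs 0.5D.

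- D = 0.02 (the 50% case): true variance per facility 0.02 + 0.078 = 0.098; model 2 × 0.259 × 0.02 + 0.078 = 0.088.
- D = 0.04 (the 0% case): 0.04 + 0.076 = 0.116; model 2 × 0.259 × 0.04 + 0.076 = 0.097.

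On 96 degrees of freedom, simulated size is about 6% and 7%. A comparison of facility mean changes on 48 degrees of freedom holds about 5.0% in both cases.

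**The case against.** The strongest reply is that the plan lists what the random effects include without saying that nothing else will be added, and that it states an intention to handle clustering. That stands in part: a facility effect varying over time is unnamed, not excluded. A reader might infer that the plan has ruled it out or ignored clustering; the text supports neither. But the term that decides the error rate would then be chosen after the data are seen. Flexible residual covariance does not settle this, because such structures normally act within a resident and do not link the changes of different residents. Residual checks could reveal drift but commit to no action.

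The second reply is that drift may be small. Outcomes are collected by trained, blinded assistants, partly from charts and their own observation, with inter-rater checks on 10% of measures. Staff informants may differ between residents of one home, which adds individual noise and not a shared shift. Tailoring applies to one arm, and if the intervention does nothing in any facility, tailoring creates no drift. All of this stands. It limits the size of the problem; it does not put shared change into the error term.

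A reader might also take 10%-13% as the expected error rate. The documents do not support that. It requires no persistent facility differences at all, and the 0.02 in Sample Size describes outcome levels, not change.

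**Conclusion.** The point holds, conditionally. On the plain reading of the model, the tested interaction has no protection against changes shared within a facility. The planned test keeps its level only if there are none, which the documents neither state nor support with a figure. With drift in both arms, the 12-month test runs at about 5.5%-6.0% for 80%-90% stability and 7.7% for 50%, with 10.4% as the extreme. Interval coverage falls to match: 94.5%-94.0%, 92.3% and 89.6%. Drift in one arm gives less.

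These sizes rest on the intercept-only reading, the planning values 0.02 and 0.6, and the assumed stable share. The point covers only the continuous resident outcomes. The facility-level H2 models are not affected in this way, and no claim is made about the Poisson models.

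**What to change.** In Data Analysis, Effectiveness, for the continuous resident-level models, state that the facility random effect varies over baseline, 4 and 12 months, with a covariance that does not force equal, independent variances (for example unstructured or heterogeneous). Fit by REML, with Kenward-Roger or between-within degrees of freedom based on the number of facilities: about 48 for a single contrast, fewer if facilities withdraw. REML is likelihood-based, so the plan's missing-at-random reasoning is unchanged.

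Alternatively, test the 12-month contrast by comparing facility mean changes between arms on 48 degrees of freedom, as the primary test or a stated check. It is also a sensible fallback if the richer model does not converge, since facility variances near 0.02 are hard to estimate. It covers only the 12-month contrast and, using residents measured at both visits, relies more heavily on the dropout assumptions.

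The cost is one sentence and no new data. With no drift the facility-level interval is about 2.6% wider from the critical value alone (2.011/1.960 = 1.026). With drift the interval widens by roughly the SD/SE ratio in the table as well, and power falls accordingly; the power that the planned test appears to keep there is partly bought by its inflated size.
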